8.5.2.3. Visit 2 /Second Vaccination (Day 28 ± 2 days)

The following activities will be performed:

- The investigator will ask all subjects about any adverse experiences occurring since Visit 1. All adverse experiences will be documented in the CRF
- Physical examination including body temperature measured axillarily
- Pregnancy test in females capable of bearing children.
- Second vaccination: for details see above
- Post vaccination observation period (30 minutes): for details see above

8.5.2.4. Visit 3 /1. Evaluation of cellular immunity (Day 35, 7 ± 2 days after the second vaccination)

The following activities will be performed:

- The investigator will ask all subjects about any adverse experiences occurring since Visit 2. All adverse experiences will be documented in the CRF.
- Blood draw of 40 ml for determination of cellular immunity

8.5.2.5. Visit 4 /1. Evaluation of humoral immunity (Day 56, 28 ± 7 days after the second vaccination)

The following activities will be performed:

- The investigator will ask all subjects about any adverse experiences occurring since Visit 3. All adverse experiences will be documented in the CRF.
- Blood draw of 10 ml for serum antibody determination (NT, ELISA)
- Pregnancy test in females capable of bearing children.

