8.5.2.2. Visit 1 /First Vaccination (Day 0)

The following activities will be performed before vaccination only when Visit 0 and Visit 1 are not the same day

- Review of inclusion and exclusion criteria
- Medical history update
- Physical examination including body temperature measured axillary
- Pregnancy test in females capable of bearing children.

Then the subject will receive the first vaccination. For vaccination the following procedures have to be considered:

- The vaccine has to reach room temperature before administration of the vaccine
- The vaccine has to be shaken vigorously for five to ten seconds
- The injection site has to prepared according to standard clinical procedures
- After removement of the protecting cap from the needle the 0.5 ml dose of the vaccine has to be administered immediately by intramuscular injection into the musculus deltoideus in the upper arm.

Following vaccination, the subject will be oserved for at least 30 minutes. Any infection site reactions and systemic adverse experiences will be recorded.

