8.5.2.6. Visit 5 /1. Evaluation of immune status (Day 84 ± 14 days)

The following activities will be performed in HSCT patients only:

- The investigator will ask all subjects about any adverse experiences occurring since Visit 4. All adverse experiences will be documented in the CRF.
- Blood draw of 10 ml for immune status and quantitative immunoglobulin levels
- Pregnancy test in females capable of bearing children.

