8.5.2.7. Visit 6 /3. Vaccination and evaluation of immune status (Day 270-365)

The following activities will be performed:

- The investigator will ask all subjects about any adverse experiences occurring since Visit 5. All adverse experiences will be documented in the CRF.
- Physical examination including body temperature measured axillary.
- Pregnancy test in females capable of bearing children.
- Third vaccination: for details see Visit 1.
- Post vaccination observation period (30 minutes): for details see Visit 1.
- Blood draw of 10 ml for immune status and quantitative immunoglobulin levels

8.5.2.8. Visit 7 /2. Evaluation of cellular immunity (Day 277-372, 7 ± 2 days after the third vaccination)

The following activities will be performed in HSCT patients only:

- The investigator will ask all subjects about any adverse experiences occurring since Visit 6. All adverse experiences will be documented in the CRF.
- Blood draw of 40 ml for cellular immunity

8.5.2.9. Visit 8 /2. Evaluation of humoral immunity (Day 298-393, 28 ± 7 days after the third vaccination)

The following activities will be performed in HSCT patients only:

- The investigator will ask all subjects about any adverse experiences occurring since Visit 7. All adverse experiences will be documented in the CRF.
- Blood draw of 10 ml for serum antibody determination (NT, ELISA)
- Pregnancy test in females capable of bearing children.

After this visit, the patients will have completed the study.

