9. SAFETY DEFINITIONS AND REPORTING REQUIREMENTS

9.1 Adverse events (AEs)

9.1.1 Summary of known and potential risks of the study drug

The following side effects have to be considered:

- very common (>1/10): local reactions at the site of injection, transient redness, and swelling.

- common (>1/100;<1/10): systemic reactions including fever, fatigue, headache, muscular pain, arthralgia. These side-effects usually occur within 72 hours after the vaccination, abate within 1-2 days, but do not acquire any medical treatment. All adverse events will be listed in the study documents and have to evaluated by the investigator for causality to the vaccination. After venous puncture local reactions, a hematoma or phlebitis can occur. However, the planed venous punctures withdraw only minor volumes of blood and do not impair the patient's health.

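### Beyond the 30-minute observation, reactions to dose 1 are first asked about on Day 26-30 and, under section 8.5.2, controls have no scheduled question about reactions to dose 3

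*Combined protocol and SAP*

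**What the plan says.** The synopsis names one tolerability/safety endpoint, a count of subjects who have a systemic reaction to the vaccine. Its statistical methodology places safety data among the secondary endpoints, to be described only.

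Section 9.1.1 (and 8.4) lists fever, fatigue, headache, and muscle and joint pain as common, meaning above 1/100 and below 1/10. On timing it says: "These side-effects usually occur within 72 hours after the vaccination, abate within 1-2 days".

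Collection of these reactions is set out visit by visit:

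- **Dose 1 (8.5.2.2):** "Following vaccination, the subject will be oserved for at least 30 minutes", and "Any infection site reactions and systemic adverse experiences will be recorded". The same observation follows doses 2 and 3.
- **Visit 2 (8.5.2.3, Day 28 ± 2):** "The investigator will ask all subjects about any adverse experiences occurring since Visit 1".
- **Visits 3 and 4 (8.5.2.4, 8.5.2.5):** all subjects are asked again, 7 ± 2 and 28 ± 7 days after dose 2.
- **Visit 5 (8.5.2.6, Day 84 ± 14):** "The following activities will be performed in HSCT patients only". Sections 8.5.2.8 (Visit 7) and 8.5.2.9 (Visit 8) open with the same restriction.
- **Visit 6 (8.5.2.7, dose 3):** "The investigator will ask all subjects about any adverse experiences occurring since Visit 5".
- **Table 1:** adverse events are marked at every visit from 1 to 8, with no limit by group.

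Section 9.5 requires a start and an end, each with date and time, for every event. The text available for review describes no diary, telephone contact or solicited-reaction window.

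**The concern.** The reactions that the safety endpoint counts are brief and often mild, and the schedule does not look for them while they happen. After dose 1 a subject leaves the clinic after half an hour and is not due to be asked anything for about four weeks. A single day of fatigue or low fever may be forgotten or misdated by then. It is also unlikely to yield the onset and end times that section 9.5 requires, or the time sequence on which the causality grades in section 9.4 rest. Body temperature is scheduled only at screening and at Visits 1, 2 and 6, so fever, a named reaction, is not measured in the days when it is expected.

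After dose 3 the difficulty is between the groups. If controls do not attend Visits 7 and 8, their later reactions reach the record only if they volunteer them, whereas HSCT patients are asked. A side-by-side table of reactions would then compare two different methods of collection.

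**Working it through.** The plan gives no figure for ascertainment that could be reproduced. Its one calculated figure, the sample size, concerns NT seroconversion and does not enter here. The check is date arithmetic on the visit windows.

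**When a usual reaction is over (9.1.1).** Onset by day 3, plus 1 to 2 days: 3 + 1 = Day 4 to 3 + 2 = Day 5 after the dose.

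**First scheduled question after the 30-minute observation.**

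| Dose | HSCT patients | Controls, section 8.5.2 | Controls, Table 1 |
|---|---|---|---|
| 1 | Day 26-30 (28 ± 2) | Day 26-30 | Day 26-30 |
| 2 | 5-9 days (7 ± 2) | 5-9 days | 5-9 days |
| 3 | 5-9 days (7 ± 2) | none | 5-9 days |

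**Interval from a reaction ending on Day 5 to the question.**

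- Dose 1: 26 − 5 = 21 to 30 − 5 = 25 days.
- Dose 2 (and dose 3 in HSCT patients): 5 − 5 = 0 to 9 − 5 = 4 days.
- The dose 1 question therefore comes about 28 − 7 = 21 days later than the dose 2 question (range 26 − 9 = 17 to 30 − 5 = 25).

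**How many reactions are at issue.** Assume that the documented frequency applies per dose, to any systemic reaction, and to both groups. The protocol states none of these three things. With 26 subjects per group, 26 × 0.01 = 0.26 to 26 × 0.10 = 2.6 subjects are expected to react after a dose. If a fraction *s* of reactions is still reported at four weeks, the recorded number is 26 × rate × *s*. The documents give no value for *s*. Purely as an illustration, an assumed *s* of 0.5 to 1 gives 0.13-0.26 subjects at the 1% rate and 1.3-2.6 at the 10% rate.

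**The Visit 6 look-back in controls.** Under 8.5.2.6 controls have no Visit 5. Read literally, the time from their Visit 4 to the Visit 5 date is never asked about.

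- Nominally this runs from Day 56 to Day 84, or 28 days.
- With windows, Visit 4 falls on Day 26 + 21 = 47 to 30 + 35 = 65, and Visit 5 on Day 84 − 14 = 70 to 84 + 14 = 98. The gap is 70 − 65 = 5 to 98 − 47 = 51 days.

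Dose 2 is given on Day 26-30, so a usual reaction to it is over by Day 30 + 5 = 35, before the earliest Visit 4 (Day 47). It has been asked about at Visits 3 and 4 in everyone. Dose 3 comes no earlier than Day 270. No vaccine reaction of the usual timing falls in the gap.

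**The case against.** This is a pilot immunogenicity study of a vaccine registered for more than a decade. Safety is described and not tested, no comparison between doses is planned, and adverse events are asked about repeatedly. A diary may look like a matter of preference. This stands as a limit on severity. It does not remove the point, because a subject who reacts only to dose 1 and forgets it is lost from the endpoint count whether or not doses are compared.

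The restriction of Visits 7 and 8 to HSCT patients may be a drafting slip. Section 7 limits only the immune-reconstitution samples to HSCT recipients, section 7.1.5 defines completion by Visit 8 for any subject, and Table 1 has no group limit. If controls do attend, the unevenness after dose 3 disappears and the dose 1 delay remains. The documents do not settle which reading governs.

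Consent pages are not part of the material reviewed, so a diary described only there cannot be excluded.

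Three stronger readings are tempting, and the documents do not support them:

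- A reader might infer that the Visit 6 wording loses vaccine reactions in controls. It does not; the period concerned starts well after dose 2 reactions have been asked about.
- A reader might infer that the long recall after dose 1 biases the comparison of groups. The delay is the same in both groups. Background fever or fatigue in HSCT patients could be misdated in either direction, and nothing in the documents quantifies it.
- A reader might infer that the count is too low by some stated fraction. No recall rate is given, and section 9.1.1 says only that reactions *usually* follow the short course.

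**Conclusion.** The point holds and should be acted on, as a cheap improvement to a stated safety endpoint. After dose 1 the endpoint may be under-counted, because the first scheduled question comes 21-25 days after a reaction of the usual course has ended. After dose 3 it is unevenly ascertained between groups if section 8.5.2 governs attendance, and evenly if Table 1 does.

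The number of reactions lost cannot be derived. At the documented frequency so few are expected that one or two forgotten events could change the reported picture, but that frequency may not carry over to HSCT recipients. The Visit 6 wording is a separate and smaller defect, confined to other adverse events in controls. Nothing here touches the NT primary endpoint, its Fisher's exact test, or the 26 per group.

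**What to change.** 1. Give every subject in both groups a one-page diary at Visits 1, 2 and 6 covering 7 days: the reactions named in 9.1.1, with start and end, plus a daily temperature. Count the safety endpoint from these windows and report it by dose and group.
2. Have the card returned at the next visit. Visits 3 and 7 can fall on day 5 or 6 after the dose; in that case the card is kept until day 7 and returned at the following visit. Controls have no later visit after dose 3 under section 8.5.2, so provide prepaid mail return for them.
3. Change the Visit 6 question to ask about events *since the last attended visit*.
4. Reconcile Table 1 with sections 8.5.2.6, 8.5.2.8 and 8.5.2.9 on which visits controls attend.

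The cost is 52 × 3 = 156 printed cards, up to 26 prepaid envelopes, one CRF page, and submission of the amendment under section 13.2.1. No extra visit is needed. The downside is a slight burden on subjects and probably a higher recorded rate of mild reactions.

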8.5.2.6. Visit 5 /1. Evaluation of immune status (Day 84 ± 14 days)

The following activities will be performed in HSCT patients only:

- The investigator will ask all subjects about any adverse experiences occurring since Visit 4. All adverse experiences will be documented in the CRF.
- Blood draw of 10 ml for immune status and quantitative immunoglobulin levels
- Pregnancy test in females capable of bearing children.

8.5.2.7. Visit 6 /3. Vaccination and evaluation of immune status (Day 270-365)

The following activities will be performed:

- The investigator will ask all subjects about any adverse experiences occurring since Visit 5. All adverse experiences will be documented in the CRF.
- Physical examination including body temperature measured axillary.
- Pregnancy test in females capable of bearing children.
- Third vaccination: for details see Visit 1.
- Post vaccination observation period (30 minutes): for details see Visit 1.
- Blood draw of 10 ml for immune status and quantitative immunoglobulin levels

8.5.2.8. Visit 7 /2. Evaluation of cellular immunity (Day 277-372, 7 ± 2 days after the third vaccination)

The following activities will be performed in HSCT patients only:

- The investigator will ask all subjects about any adverse experiences occurring since Visit 6. All adverse experiences will be documented in the CRF.
- Blood draw of 40 ml for cellular immunity

8.5.2.9. Visit 8 /2. Evaluation of humoral immunity (Day 298-393, 28 ± 7 days after the third vaccination)

The following activities will be performed in HSCT patients only:

- The investigator will ask all subjects about any adverse experiences occurring since Visit 7. All adverse experiences will be documented in the CRF.
- Blood draw of 10 ml for serum antibody determination (NT, ELISA)
- Pregnancy test in females capable of bearing children.

After this visit, the patients will have completed the study.

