9.1.2 DEFINITION OF ADVERSE EVENTS	27
9.2 SERIOUS ADVERSE EVENTS (SAES)	28
9.2.1 HOSPITALIZATION – PROLONGATION OF EXISTING HOSPITALIZATION	29
9.2.2 SAES RELATED TO STUDY-MANDATED PROCEDURES	29
9.2.3 SUSPECTED UNEXPECTED SERIOUS ADVERSE REACTIONS (SUSARS)	29
9.2.4 PREGNANCY	30
9.3 SEVERITY OF ADVERSE EVENTS	30
9.4 RELATIONSHIP TO STUDY DRUG	31
9.5 REPORTING PROCEDURES	32

Nr 2011-002928-41	
9.5.1 REPORTING PROCEDURES FOR SAES	32
9.5.2 REPORTING PROCEDURES FOR SUSARS	33
9.5.3 ANNUAL SAFETY REPORT	34
10. FOLLOW-UP	34
11. STATISTICAL ANALYSIS	34
11.1 SAMPLE SIZE CONSIDERATIONS	34
11.2 RELEVANT PROTOCOL DEVIATIONS	35
11.3 ENDPOINTS ANALYSIS	35
11.4 MISSING, UNUSED AND SPURIOUS DATA	35
11.5 INTERIM ANALYSIS	35
11.6 SOFTWARE PROGRAM(S)	35
12. DOCUMENTATION AND DATA MANAGEMENT	35
12.1 DOCUMENTATION OF STUDY RESULTS	35
12.1.1 CASE REPORT FORM (CRF)	36
12.1.2 DATA COLLECTION	36
12.2 SAFEKEEPING	36
12.3 QUALITY CONTROL AND QUALITY ASSURANCE	37
12.3.1 PERIODIC MONITORING	37
12.3.2 AUDIT AND INSPECTIONS	38
12.4 REPORTING AND PUBLICATION	38
12.4.1 PUBLICATION OF STUDY RESULTS	38
13. ETHICAL AND LEGAL ASPECTS	38
13.1 INFORMED CONSENT OF SUBJECTS	38
13.2 ACKNOWLEDGEMENT / APPROVAL OF THE STUDY	39
13.2.1 CHANGES IN THE CONDUCT OF THE STUDY	39
13.3 INSURANCE	40
13.4 CONFIDENTIALITY	40
13.5 ETHICS AND GOOD CLINICAL PRACTICE (GCP)	40
14. APPENDICES	41
15. REFERENCES	42

TABLE 1. VISIT AND ASSESSMENT SCHEDULE

PERIODS	Name	SCREENING	VACCINATION 44-56 weeks							
	Duration									
VISITS	Number	1	2	3	4	5	6	7	8	9
	Name	Screening	Visit 1/ 1 st Vaccination	Visit 2/ 2 nd Vaccination	Visit 3	Visit 4	Visit 5	Visit 6/ 3 rd Vaccination	Visit 7	Visit 8
	Time	Day – 28	Day 0	Day 28 (± 2 days)	Day 35 (7 ± 2 days after Visit 2)	Day 56 (28 ± 7 days after Visit 2)	Day 84 (± 14 days)	Day 270- 365	Day 277-372 (7± 2 days after Visit 6)	Day 298-393 (28 ± 7 days after Visit 6)
Informed Consent X		Х								
Inclusion / Exclus	ion Criteria	Х	Х							
Medical History		Х	Х							
Physical Examina	tion	Х	Х	Х				Х		
Pregnancy Test		Х	Х	Х		Х	Х	Х		Х
Blood Draw (Sero	logy)	Х				Х				Х
Blood Draw (Cellular immunity)		Х			Х				Х	
Blood Draw (Imm reconstitution + s immunoglobulin	erum	х					х	х		
Vaccination			Х	Х				Х		
Adverse Events			Х	Х	Х	Х	Х	Х	Х	Х

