7. STUDY DESIGN

A prospective open-label phase II pilot study will be performed. A total of 52 adult male or female subjects, 26 HSCT patients (study population) and 26 healthy volunteers (control group), will be enrolled in this clinical trial. Eight study visits per patient will be planed. Eligible patients will receive at least two TBE vaccinations (study visit 1 – day 0, study visit 2 -1month after the first vaccination) with a total of two doses of the TBE vaccine FSME IMMUN®. Whenever possible, the patients will receive complete primary vaccination with a third dose of TBE vaccine FSME IMMUN® (study visit 9 - 12 months after the first vaccine will be injected intramuscularly in the Musculus deltoideus.

FSME IMMUN® contains formalin-inactivated TBE virus. One dose (0.5 ml) contains 2.4 µg of antigen inactivated by formaldehyde. Human albumin is used as stabilizer and aluminium hydroxide is used as adjuvant. The vaccine contains traces of formaldehyde, protamine sulphate, neomycin and gentamicin.

Serum samples for determination of antibody levels will be obtained immediately before the first (study visit 1), 4 weeks after the second vaccination (study visit 4), and four weeks after the third vaccination (study visit 8). Blood samples for the analysis of cellular immunity will be taken before the first (study visit 1), one week after the second vaccination (study visit 3) and one week after the third vaccination (study visit 7). Blood samples for determination of the immune reconstitution and the quantitative immunoglobulin levels will be obtained prior to the first (study visit 1) and third vaccination (study visit 6) and 12 weeks after the first vaccination (study visit 5) in HSCT recipients only.

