7.1.4 Study duration

The total study duration is estimated to be four years. For the individual study participant the study duration will be 44-56 weeks.

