7.1.5 Withdrawal and replacement of subjects

Criteria for withdrawal

Subjects may prematurely discontinue from the study at any time. Premature discontinuation from the study is to be understood when the subject did not undergo complete the last visit (study visit 8) and / or all pivotal assessments during the study.

Subjects must be withdrawn under the following circumstances:

- at their own request
- if the investigator feels it would not be in the best interest of the subject to continue
- if the subject violates conditions laid out in the consent form / information sheet or disregards instructions by the study personal

In all cases, the reason why subjects are withdrawn must be recorded in detail in the CRF and in the subject's medical records. Should the study be discontinued prematurely, all study materials (complete, partially completed and empty CRFs) will be retained.

Follow-up of patients withdrawn from the study

In case of premature discontinuation after start of vaccination, no further investigations concerning the study will be performed. Furthermore, participants may request that from the time point of withdrawal no more data will be recorded and that all biological samples collected in the course of the study will be destroyed.

Replacement policy

If the week 8 (primary endpoint) is reached, drop-outs will be included in the sample size. If the participiant drops out before the week 8 is reached, patients will be replaced and the next free subject number will be allocated.

7.1.6 **Premature termination of the study**

The sponsor has the right to close this study at any time. The IEC and the competent regulatory authority must be informed within 15 days of early termination.

The trial or single dose steps will be terminated prematurely in the following cases:

- If adverse events occur which are so serious that the risk-benefit ratio is not acceptable.
- If the number of dropouts is so high that proper completion of the trial cannot realistically be expected.

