8.1.1 Dosage and administration

Initial dose: All subjects will receive one dose 0.5 ml TBE vaccine FSME IMMUN on day 0 (study visit 1).

Repeated dose: All subjects will receive one additional dose 0.5 ml TBE vaccine FSME

IMMUN on week 4 (study visit 2) and between week 40-52 (study visit 6).

Route of administration: TBE vaccine will be injected intramuscularly in the Musculus deltoideus.

Duration: All subjects will receive 0.5 ml TBE vaccine three times within one year.

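### The visit text limits Visits 7 and 8 to HSCT patients, although controls also get dose 3 and other sections carry them through to Visit 8

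*Combined protocol and SAP*

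**What the plan says.** **Who receives dose 3.** Section 8.1.1: "All subjects will receive 0.5 ml TBE vaccine three times within one year". Section 7 is softer: "Whenever possible, the patients will receive complete primary vaccination with a third dose". Visit 6, where dose 3 is given, has no group limit.

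**What happens after dose 3.** On the day itself, Visit 6 lists: "Post vaccination observation period (30 minutes): for details see Visit 1". Its adverse-event question looks back to Visit 5, so it covers the time before the dose. The questions about the time after dose 3 are at Visit 7 (one week later) and Visit 8 (four weeks later), and each of these visits is headed: "The following activities will be performed in HSCT patients only". Visit 7 also holds the cellular-immunity draw, and Visit 8 the serum draw for NT and ELISA. Section 10 requires no follow-up after that.

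**What other sections say.**
- Section 7.1.4: "For the individual study participant the study duration will be 44-56 weeks".
- Section 7.1.5 defines premature discontinuation as the case "when the subject did not undergo complete the last visit (study visit 8".
- Section 7 schedules the Visit 7 and Visit 8 samples without naming a group. It attaches a limit only to immune reconstitution and immunoglobulins, ending: "12 weeks after the first vaccination (study visit 5) in HSCT recipients only". Section 8.5.4.2 draws the same line.
- The synopsis counts protective antibody responses after both the second and the third vaccination. Its tolerability endpoint counts subjects with systemic reactions and does not say whether this is per dose or over all doses.

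**The concern.** Two parts of one protocol give the site opposite instructions for half of the participants. If the visit text is followed, controls receive a study vaccination and are then neither questioned nor sampled.

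The larger loss is immunogenicity. The primary objective compares humoral response with healthy volunteers, and the synopsis efficacy endpoint extends to the third vaccination. Without control sera at Visit 8 and control cells at Visit 7, the NT, ELISA and cellular results after dose 3 have no comparator.

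The smaller loss is safety. Section 9.1.1 expects systemic reactions mostly in the first three days, after the 30-minute observation has ended. A count over all doses would then draw on three questioned doses in HSCT recipients and two in controls.

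**Working it through.** **1. Reproduce the stated duration.** Section 8.1.1 puts dose 3 at week 40-52, and Visit 8 follows four weeks later: 40 + 4 = 44 and 52 + 4 = 56. This gives the stated 44-56 weeks. A control who stopped at Visit 6 would finish at week 40-52.

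Two checks on this match:
- The day windows are slightly looser. Visit 6 on day 270-365 is week 38.6-52.1, and Visit 8 on day 298-393 is week 42.6-56.1. The exact match is with the weeks in section 8.1.1.
- Four weeks of screening plus week 40-52 would also give 44-56. That reading fails for HSCT patients, who do attend Visit 8: counted from screening, they would need 4 + 40 + 4 = 48 to 4 + 52 + 4 = 60 weeks. The synopsis also calls the 44-56 weeks the active phase. One figure is given for every participant, so it runs from dose 1 to Visit 8.

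**2. Set the sections side by side.**

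| Source | Controls at Visits 7 and 8? |
|---|---|
| 8.5.2.8 and 8.5.2.9, visit headers | No |
| 7.1.4, duration | Yes, by step 1 |
| 7.1.5, discontinuation | Yes; otherwise all 26 controls discontinue by design |
| 7 and 8.5.4.2, samples and endpoints | Yes; the group limit is placed elsewhere |
| Table 1 | Cannot tell; it shows no groups |

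The labels in the visit text look misplaced elsewhere too. The immune-status draw at Visit 6 carries no restriction there, although section 7 limits it to HSCT recipients.

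**3. Doses without a later enquiry, if the visit text is followed.** Planned control doses: 26 × 3 = 78. Control third doses: up to 26, so 26/78 = 33%. Of all planned doses, 26/156 = 17%. These are maxima, because uptake of dose 3 may be incomplete. The same 26 controls would lose one cellular and one serum sample each.

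**4. Effect on the count of subjects with a systemic reaction.** Assumptions:
- the same true rate p per dose in both groups;
- independence between doses;
- no control reaction to dose 3 recorded, either in the 30 minutes or spontaneously;
- counting over all doses;
- a share u of HSCT recipients receiving dose 3, assumed to range from 1.0 to 0.6.

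Section 9.1.1 classes these reactions between 1/100 and 1/10.

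- Expected HSCT count: 26 × [1 − (1 − p)²(1 − up)]
- Expected control count: 26 × [1 − (1 − p)²]
- Gap: 26 × u × p × (1 − p)²
- SD of the difference at u = 1: √(26 × [pH(1 − pH) + pC(1 − pC)]), where pH and pC are the two bracketed probabilities

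| p | HSCT, u = 1 | Control | Gap, u = 1 | Gap, u = 0.8 | Gap, u = 0.6 | SD |
|---|---|---|---|---|---|---|
| 1% | 0.77 | 0.52 | 0.25 | 0.20 | 0.15 | 1.12 |
| 5% | 3.71 | 2.54 | 1.17 | 0.94 | 0.70 | 2.34 |
| 10% | 7.05 | 4.94 | 2.11 | 1.68 | 1.26 | 3.02 |

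The gap is zero if the same subjects react at every dose, or if controls attend Visits 7 and 8.

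**The case against.** The strongest reply is that the late visits are HSCT-only by design. Section 6 states the aims for adult HSCT recipients, section 6.2 frames the cellular objective for them, the secondary NT endpoint compares dose 3 with dose 2 rather than group with group, and the only planned test is at Visit 4. The label also appears at both visits, not once. This is a coherent design and cannot be excluded. It does not explain sections 7, 7.1.4 or 7.1.5, and it gives no reason to vaccinate controls a third time without asking about reactions. Under either intention some text must change.

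Four stronger readings are tempting, and the documents do not support them.

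- *Table 1 proves that controls attend.* It marks Visits 7 and 8 with no group limit, but it shows Visit 5 and the immune-status draws in the same way, and those are for HSCT patients only. It is weak support at best.
- *Control reactions after dose 3 cannot be captured at all.* The 30-minute observation records reactions, and section 9.1.2 defines an adverse event by its occurrence during the study, not by being elicited at a visit. Spontaneous reports remain possible. Reactions that are never reported are lost.
- *The HSCT reaction count is irreparably inflated.* Section 9.5 records the start date and time of each event, so reporting by dose, or for doses 1 and 2 only, removes the imbalance.
- *All controls become drop-outs and the primary analysis suffers.* Section 7.1.5 keeps drop-outs after week 8 in the sample, and section 11.3 includes eligible subjects with available antibody responses. The discontinuation status would be nominal.

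**Conclusion.** The point stands as a contradiction about who attends Visits 7 and 8, and the weight of the text favours both groups attending. The label is more likely a drafting error than a design choice, but that is an inference.

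The consequence depends on which text the site follows. If it follows the visit headers, the main loss is every planned control sample after dose 3, which leaves the third-vaccination endpoints without a comparator. The tolerability effect, at most about 2 of 26 subjects under the assumptions above, is below the sampling SD of the group difference at every rate examined. Safety is descriptive, and no between-group safety test is planned. If controls attend both visits, nothing is lost. The primary comparison at Visit 4 and the sample size are the same either way.

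**What to change.** Delete the HSCT-only header from the Visit 7 and Visit 8 text. Add one sentence to section 11.3, whose list of descriptive analyses currently omits safety: *Systemic reactions will be reported by group after each vaccination, among subjects who received that dose.* No new CRF field is needed.

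If the restriction was intended, keep the headers and instead correct sections 7, 7.1.4 and 7.1.5, mark the groups in Table 1, and limit between-group safety and immunogenicity descriptions to doses 1 and 2.

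Cost of the main fix: up to 26 control contacts at each of two visits (52 in all) and 40 + 10 = 50 ml of blood per control. Sections 7 and 7.1.4 already imply this attendance, but it is a real burden if the sponsor had not planned it. By-dose cells will be small: with 0 events in 26, the two-sided 95% upper limit is 1 − 0.025^(1/26) = 13.2%.
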